9.4 FUTURE USE OF SAMPLES

Samples for PK will be stored until final clinical study report is issued. Thereafter they will be discarded. Samples for immunogenicity will be stored for longer time period if necessary dependent on whether issues related to immunogenicity occurs in the study. The timeframe will be defined after the availability of immunogenicity results.

9.5 APPROPRIATENESS OF MEASUREMENTS

SAR425899 is a dual agonist of the GLP-1 and glucagon receptors, and is being developed for the treatment of patients with T2DM who are overweight/obese. Preclinical studies have demonstrated reductions in blood glucose and body weight as well as increase in energy expenditure with SAR425899 administration.

The primary objective of this study is the change in HbA1c from baseline to Week 26.

Several studies have documented a reduced risk for the development and progression of complications of type 2 diabetes, when HbA1c values are lowered. HbA1c is the benchmark for the overall glycemic control and is strongly correlated with FPG and PPG levels. Therefore, diabetes management strategies recommend strict glycemic control with an HbA1c <7% according to the American Diabetes Association (ADA) and European Association for the Study of Diabetes (EASD), and a more stringent goal of <6.5% for appropriate patients. The duration of study treatment is considered to be sufficient for achieving stable conditions with IMP and for enabling an adequate assessment of time-dependent changes in HbA1c.

The problem of weight gain in type 2 diabetes is widely recognized. More than 80% of individuals with type 2 diabetes are overweight, many at the time of diagnosis. Consequently, iatrogenic weight gain is not only unwelcome, but represents an important clinical issue that can become a barrier to the successful management of glycemic control. Recently, the phase 1 study (TDR13700) conducted in both healthy volunteers and patients with T2DM was completed. The effect of SAR425899 on glucose lowering and weight reduction was observed in the study.

A number of biomarkers will be integrated into the trial, as these markers may serve to better understand the mechanism of action (MoA) of dual agonism and confirm that target receptors were hit. For glucagon effects on lipid metabolism and lipolysis have been described.

Increased heart rate has been linked to cardiovascular diseases. BNP and hs-CRP are added as biomarkers to evaluate the risk of cardiovascular diseases (20).

The therapeutic potential of GLP-1 analog in the treatment of NASH has been suggested recently. The change of NASH biomarkers will be evaluated in the study (21).

10 STUDY PROCEDURES

10.1 VISIT SCHEDULE

The visit schedule and procedures/assessments listed in the study flow chart in [Section 1.2](#) are not repeated in this section.

The aim of this section is to provide details on how some of the procedures/assessments have to be performed.

The study consists of 10 on-site visits and 3 phone-call visits.

The patient has to be fasting for all on-site visits. For all these visits, the patient should be seen in the morning, at approximately the same time, as far as possible.

The fasting condition is defined as an overnight fast no less than 8 hours that consisted of no food or liquid intake, other than water. The IMP and other glucose-lowering agents (ie, metformin) should be administered after the fasting blood sample is drawn for all laboratory tests on the study site.

Note: If the patient is not fasting at the visits specified above, the blood sample will not be collected and a new appointment should be given to the patient for the following day if possible, with instruction to be fasted.

Visit window: during the screening period and for randomization visit a visit window of ± 3 days is acceptable. During the treatment period a visit window of ± 3 days is acceptable between Visit 4 (Week 0) and Visit 9 (Week 8), and a visit window of ± 5 days is acceptable from Visit 10 (Week 14) to Visit 12 (Week 26). A visit window of -1 days or +3 days for the post-treatment follow up visit (V13) is acceptable using the day of V12 as reference. If one visit date is changed, the next visit should occur according to the original schedule.

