8.8.2 Rescue therapy

In case of FPG or HbA1c above pre-defined thresholds and if no reasons can be found for insufficient glucose control, it is recommended to add rescue therapy.

Central laboratory alerts on FPG and HbA1c are set up to ensure that glycemic parameters remain under predefined threshold values (see hereinafter).

The threshold values are defined as follows, depending on study period:

From baseline Visit 4 (Week 0) to Visit 9 (Week 8, including value at Visit 9): FPG >270 mg/dL (15.0 mmol/L).

From Visit 9 (Week 8) to Visit 10 (Week 14): FPG > 240 mg/dL (13.3 mmol/L).

From Visit 10 (Week 14) to Visit 12 (Week 26): FPG>200 mg/dL (11.1 mmol/L) or HbA1c>8%.

In case of FPG / HbA1c above the threshold values, the investigator should ensure that no reasonable explanation exists for insufficient glucose control, and in particular that:

- Plasma glucose was actually measured in fasting condition (ie, after at least 8 hrs fast).
- Investigational product is given at planned dose.

- There is no intercurrent disease, which may jeopardize glycemic control (eg, infectious disease).
- Compliance with treatment is appropriate.
- Compliance with diet and lifestyle is appropriate.

If any of the above can reasonably explain the insufficient glycemic control, the investigator should undertake appropriate action, ie,

- Dose increase of investigational product according to protocol (if tolerance allows).
- Set up adequate investigation and treatment of intercurrent disease (to be reported in AE/concomitant medication parts of the eCRF).
- Stress on the absolute need to be compliant with treatment.
- Organize a specific interview with a Registered Dietician or other qualified nutrition professional and stress on the absolute need to be compliant to diet and lifestyle recommendations, and check a FPG / HbA1c assessment at the next visit.

If none from the above-mentioned reasons can be found, or if appropriate action fails to decrease FPG / HbA1c under the threshold values, rescue medication may be introduced.

The choice of rescue therapy is at the investigator's discretion with the exception of using GLP-1 receptor agonists or DPP4 inhibitors.

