### **2.1.3.2 Secondary efficacy endpoint(s)**

#### **Continuous secondary efficacy endpoints**

The continuous secondary efficacy endpoints are:

- Change in body weight from baseline to Week 26,
- Change in FPG from baseline to Week 26,
- Change in 7-point SMPG profiles from baseline to Week 26 (each time point and average daily value),
- Change in PPG and in blood glucose excursion in response to a standardized meal test in up to 50% subset of all patients from baseline to Week 26 at time points premeal, 10 min, 20 min, 0.5 h, 1 h, 1.5 h, 2 h, 3 h, 4 h post meal,
- Change in fasting insulin, proinsulin, and C-peptide from baseline to Week 26,
- Change in insulin, proinsulin, and C-peptide and associated excursion values in response to a standardized meal test in up to 50% subset of all patients from baseline to Week 26 at time points premeal, 10 min, 20 min, 0.5 h, 1 h, 1.5 h, 2 h, 3 h, 4 h post meal,
- Change in HOMA- $\beta$  and HOMA-IR from baseline to Week 26,
- Change in lipid profile (total cholesterol, triglycerides, LDL-C, and HDL-C) and free fatty acids, and Ketone bodies from baseline to Week 26,

For 7-point SMPG profiles, the mean daily (ie, average on 7 points) change from baseline to Week 26 will be analyzed. In addition, the change from baseline to Week 26 for each of the 7 points will be evaluated, respectively.

For FPG, only values assessed in fasting condition will be analyzed.

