##### ***Primary analysis***

The primary efficacy endpoint of change in HbA1c from baseline to Week 26 will be analyzed with missing post-baseline values imputed by placebo control-based multiple imputation (MI) method under the missing not at random framework (5, 6, 7).

- For placebo group patients, missing data will be imputed based on the placebo group data.
- For patients in the SAR425899 dose groups and liraglutide group, missing data will be imputed as if the patients were on placebo group throughout the study.

For missing HbA1c value at baseline, missing data will be imputed using MI under the missing at random (MAR) assumption. Missing data at baseline will be imputed using regression method that includes randomization stratum of screening HbA1c ( $\leq 8.0\%$ ,  $> 8.0\%$ ), randomization stratum of Visit 4 (Day 1) BMI ( $< 35.0 \text{ kg/m}^2$ ,  $\geq 35.0 \text{ kg/m}^2$ ), and baseline value in the imputation model (see sample code Part 1c in [Appendix D](#)).

The change from baseline at Week 26 values will be derived from observed or imputed Week 26 HbA1c values (see sample code Part 1a in [Appendix D](#)). Each of the complete dataset will be analyzed by the Analysis of Covariance (ANCOVA) model with treatment groups (SAR425899 0.12 mg, SAR425899 0.16 mg, SAR425899 0.20 mg, placebo and liraglutide), randomization strata of screening HbA1c value ( $< 8\%$ ,  $\geq 8\%$ ), randomization strata of Visit 4 (Day 1) BMI

(<35.0 kg/m^2, ≥35.0 kg/m^2), and country as fixed effects, and baseline HbA1c value as a covariate (see sample code Part 2 in [Appendix D](#)).

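### The fasting rule in Protocol 10.1 withholds every blood sample from a non-fasting patient, HbA1c included, so a Week 26 primary value that is never redrawn is lost needlessly

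*Protocol*

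**What the plan says.** Protocol 10.1 sets one rule for the whole schedule: "The patient has to be fasting for all on-site visits". It treats the draw as a single event, since IMP and metformin "should be administered after the fasting blood sample is drawn for all laboratory tests on the study site". The note on non-fasting arrivals reads: "If the patient is not fasting at the visits specified above, the blood sample will not be collected". The same sentence goes on to give the patient a new appointment, for the next day if possible. Visits 10 to 12 have a window of ±5 days.

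The flow chart (Protocol 1.2) schedules HbA1c at Visits 6, 8, 9, 10, 11 and 12. The HbA1c assessment method (Protocol 9.1.1.2) states no fasting condition. Antibody samples have to be taken before dosing (Protocol 9.2.2.7); fasting is not mentioned. The fasting check in the rescue section (Protocol 8.8.2) concerns plasma glucose.

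The SAP labels several measurements as fasting: insulin, pro-insulin, C-peptide and lipids (2.1.3, 2.1.4.4) and adiponectin (2.1.6). Its explicit fasting filter at analysis is stated for FPG: "For FPG, only values assessed in fasting condition will be analyzed" (2.1.3.2). No such filter is stated for HbA1c.

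SAP 2.5.4 and Table 4 assign unscheduled measurements from Day 161 onward to Visit 12 when no scheduled value exists. Imputation applies only if nothing is found. For the SAR425899 and liraglutide groups, "missing data will be imputed as if the patients were on placebo group throughout the study" (2.4.4.1). In the responder analyses a patient without a Week 26 value is a non-responder (2.4.4.2).

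**The concern.** The note withholds the primary endpoint sample from a patient who is present at the site, for the sake of other analytes drawn at the same time. Elsewhere the plan works hard to retain Week 26 HbA1c: patients are followed after stopping IMP, and values are used regardless of discontinuation or rescue. Turning away a usable sample runs against that.

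Week 26 is the most exposed visit. Visit 12 is the last on-site visit, and Visit 13 is a phone call. Visit 11 cannot stand in for it: its target of Day 140 ±5 gives Days 135 to 145, inside the Day 119 to 160 row of Table 4. A patient with no unscheduled, pre-rescue or discontinuation sample from Day 161 has nothing to fall back on.

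A value lost in an active arm pulls the estimated effect toward zero. Safety results lost at the same visit are not imputed. If the Visit 10 draw is not recovered, the HbA1c alert that applies from Week 14 has no result to act on until Visit 11, six weeks later.

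**Working it through.** **1. The conditions for a loss.** A Week 26 HbA1c reaches imputation only if all of these hold:
- the patient arrives non-fasting at Visit 12;
- the rebooking fails, and no sample is drawn within Days 177 to 187 (182 ± 5);
- no other central-laboratory value exists from Day 161 onward (Table 4 has no upper limit).

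The documents give no rate for any of these. Let m be the share of Week 26 HbA1c values in an active arm lost by this route; 1% to 5% is an assumed range. In a 60-patient arm that is 0.6 to 3 patients.

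**2. The plan's own figure.** Inputs from Protocol 11.1 and SAP 1.3: 60 versus 30 patients, difference 0.7, SD 1.1, two-sided 5%.
- Standard error = 1.1 × √(1/60 + 1/30) = 1.1 × √0.05 = 0.246.
- Noncentrality = 0.7 / 0.246 = 2.846.
- Power = 81.2% by the normal approximation and 80.4% by the noncentral t with 88 degrees of freedom.

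The stated 80% is reproduced.

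**3. Effect of lost values.** Let r be the share of the treatment effect that an imputed value retains through the patient's earlier observed HbA1c. The expected difference is then

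difference = 0.7 × (1 − m × (1 − r)),

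with the standard error held at 0.246. Placebo losses are imputed from placebo data and are taken not to shift the mean. The worst case is r = 0, where every imputed value carries no effect.

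| m | Difference, r = 0 | Power, r = 0 | Difference, r = 0.8 | Power, r = 0.8 |
|---|---|---|---|---|
| 0 | 0.700 | 80.4% | 0.700 | 80.4% |
| 1% | 0.693 | 79.6% | 0.699 | 80.2% |
| 1 in 60 | 0.688 | 79.0% | 0.698 | 80.1% |
| 2% | 0.686 | 78.8% | 0.697 | 80.1% |
| 5% | 0.665 | 76.2% | 0.693 | 79.6% |

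For example, m = 5% with r = 0 gives 0.7 × 0.95 = 0.665; with r = 0.8 it gives 0.7 × (1 − 0.05 × 0.2) = 0.693.

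**4. What the table does not cover.** The value of r cannot be read from the text, because the imputation code (SAP Appendix D) is not included in it. The figures are for one dose against placebo. The SAP's first confirmatory test is a trend contrast across the three doses and placebo (2.4.4.1), to which they do not apply directly.

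**The case against.** The strongest reply is that the note defers the sample and does not cancel it. The same sentence gives a new appointment, and the words on possibility may qualify only the next day, leaving another day open. The ±5-day window and the Day 161 allocation then stand between a non-fasting arrival and imputation. This stands, and it rules out the inference that each non-fasting Week 26 arrival loses the primary endpoint.

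Three other stronger readings also fail:
- **That the SAP regards only FPG as fasting-dependent.** It labels insulin, pro-insulin, C-peptide, lipids and adiponectin as fasting too. What can be said is that the explicit analysis filter is stated for FPG and none is stated for HbA1c.
- **That placebo-based imputation affects everything lost.** It dilutes the effect only in the SAR425899 and liraglutide groups and does not apply to safety results.
- **That full safety panels are lost at every visit.** Visit 11 schedules amylase and lipase but no hematology, liver tests, calcitonin or antibodies, and unscheduled values enter the safety analyses.

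A single fasting visit is also a coherent choice. Body weight, which is in the testing hierarchy, is measured fasting, and injection is coordinated with blood, PK and meal-test sampling (Protocol 8.1.1). The non-fasting patient has to return anyway. That justifies rebooking the fasting assessments, but not declining the HbA1c sample on the day. Finally, sampling detail sits in a laboratory manual that is not available here (Protocol 9.1) and might contain an exemption; the protocol text does not.

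**Conclusion.** The point holds as a minor gap in data collection. The protocol withholds HbA1c from non-fasting patients without stating any fasting condition for it, and Week 26 has no later scheduled draw. Most cases should be recovered.

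For values that are not, the cost in pairwise power is at most 0.8 points at 1% lost and 4.2 points at 5% lost (80.4% to 79.6% and 76.2%). It is about 0.8 points at 5% lost if 80% of the effect is retained. These figures rest on an assumed loss rate, an assumed retention and an unchanged standard error, so they bound a small loss and do not predict one. The documents do not support a claim that the trial's power is materially compromised. That HbA1c itself does not depend on fasting is general laboratory knowledge; the documents are consistent with it but do not say so. The case for change is that the loss serves no purpose for HbA1c and is cheap to prevent.

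**What to change.** Amend the note in Protocol 10.1, and the laboratory manual to match:
- A non-fasting patient still has HbA1c and the non-fasting safety and antibody samples drawn at that visit, pre-dose, with fasting status recorded.
- Only the fasting assessments are rebooked, within the visit window: FPG; fasting insulin, pro-insulin and C-peptide; lipids and free fatty acids; ketone bodies; adiponectin; the meal test; and fasting body weight.
- The central laboratory confirms which tests belong on each list.

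The new wording must be reconciled with the visit-day injection timing in Protocol 8.1.1; no dosing rule is proposed here.

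The cost is a short text change, an occasional second venipuncture, and an HbA1c dated a day or so apart from the fasting tests. No change to the SAP analysis is needed.

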9.2.2.1 Observation period of safety endpoints

The observation period of safety data will be divided into 3 segments:

- The pretreatment period is defined as the time between the date of the informed consent and the first injection of IMP.
- The on-treatment period is defined as the time from the first injection of IMP up to 3 days (1 day for hypoglycemia) after the last injection of IMP, regardless of the introduction of rescue therapy. The 3-day interval is chosen based on the half-life of the IMP (approximately 5 times the half-life of SAR425899).
- The post treatment period is defined as the time starting 4 days after last injection of IMP (after the on-treatment period).

The baseline value for safety endpoints will be the last available value prior to the first injection of IMP.

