10.1.2.2 Follow up period phone call Visit 13 (3 days FU)

During the phone call, the following questions should be asked:

- Did you experience any new medical event, disease or symptom since the last visit?
- Did you experience any change in a pre-existing medical event or disease or symptom since the last visit?
- Did you change or add any concomitant medication since the last visit?

All reports of any AEs are recorded. In case of an AE the patient may be asked to come to the investigational site, as appropriate,

All reports of hypoglycemic events (if any) are recorded, in case of a hypoglycemia the patient may be asked to come to the investigational site, as appropriate,

The use or change of any concomitant medications is reported (including rescue therapy).

Note: This visit should not be performed in case of premature treatment discontinuation.

IRT is contacted for notification of the end of study.

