10.4.3 General guidelines for reporting adverse events

- All AEs, regardless of seriousness or relationship to IMP/NIMP, spanning from the signature of the informed consent form until the end of the study as defined by the protocol for that patient, are to be recorded on the corresponding page(s) or screen(s) of the eCRF.
- Whenever possible, diagnosis or single syndrome should be reported instead of symptoms. The Investigator should specify the date of onset, intensity, action taken with respect to IMP, corrective treatment/therapy given, additional investigations performed, outcome, and his/her opinion as to whether there is a reasonable possibility that the AE was caused by the IMP or by the study procedure(s).
- The Investigator should take appropriate measures to follow all AEs until clinical recovery is complete and laboratory results have returned to normal, or until progression has been stabilized, or until death, in order to ensure the safety of the patients. This may imply that

observations will continue beyond the last planned visit per protocol, and that additional investigations may be requested by the monitoring team up to as noticed by the Sponsor.

- When treatment is prematurely discontinued, the patient's observations will continue until the end of the study as defined by the protocol for that patient.
- Laboratory, vital signs or ECG abnormalities are to be recorded as AEs only if:
 - Symptomatic and/or,
 - Requiring either corrective treatment or consultation, and/or,
 - Leading to IMP discontinuation or modification of dosing, and/or,
 - Fulfilling a seriousness criterion, and/or,
 - Defined as an AESI.

Instructions for AE reporting are summarized in [Table 6](#).

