#### *Observation period*

The observation period will be divided into 4 epochs:

- The **screening** epoch is defined as the time from the signed informed consent date up to the first administration of the IMP.
- The **treatment** epoch is defined as the time from the first administration of the IMP to the last administration of the IMP
- The **residual treatment** epoch is defined as the time from the last administration of the IMP up to 3 days (1 day for hypoglycemia, 28 days for anti-SAR425899 antibody) after the last administration of IMP.

The treatment-emergent adverse event (TEAE) period will include both **treatment** and **residual treatment** epochs.

- The **posttreatment** epoch is defined as the period of time starting the day after the end of the treatment-emergent adverse event period up to the end of the study (defined as last protocol-planned visit or the resolution/stabilization of all serious adverse events (SAE) and adverse events with prespecified monitoring as defined in protocol).

The on-study observation period is defined as the time from the start of treatment until the end of study (defined as the last scheduled visit for those who completed the study and the date collected on e-CRF page “Completion of End of Study/Follow-up” for those who did not complete the study, or the resolution/stabilization of all serious adverse events and adverse events with prespecified monitoring as defined in the protocol whichever is the latest).

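### The planned safety follow-up does not always reach the end of the plan's own 3-day treatment-emergent window: a day-2 closing call is allowed, and some early stoppers have no closing contact

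*Protocol*

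**What the plan says.** **The window.** Protocol 9.2.2.1 extends the on-treatment period "up to 3 days (1 day for hypoglycemia) after the last injection of IMP, regardless of the introduction of rescue therapy". It gives the reason: "The 3-day interval is chosen based on the half-life of the IMP (approximately 5 times the half-life of SAR425899". SAP 2.1.4 (Observation period) sets the same length for the residual treatment epoch, which belongs to the TEAE period: "up to 3 days (1 day for hypoglycemia, 28 days for anti-SAR425899 antibody) after the last administration of IMP". TEAEs are the main focus of adverse event (AE) reporting in Protocol 11.4.3.2 and SAP 2.4.5.2.

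**The closing contact.** Visit 13 (V13) is a phone call, nominally 3 days after Visit 12 (V12). Under Protocol 10.1.2.2 it asks about new or changed events, records hypoglycemia and medication changes, and triggers the end-of-study notice to the IRT. Its tolerance is in Protocol 10.1: "A visit window of -1 days or +3 days for the post-treatment follow up visit (V13) is acceptable using the day of V12".

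**The last dose in completers.** The flow chart (Protocol 1.2) marks IMP administration at V12, footnote g has the patient inject on site at on-site visits, and the meal test in Protocol 9.2.1.2.2 is timed from a V12 dose.

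**Early stop of IMP.** Protocol 10.1.2.2 says of V13: "This visit should not be performed in case of premature treatment discontinuation". Flow-chart footnote a and Protocol 8.1.1 make the same exception. These patients instead have a V12-type visit as soon as possible and then keep their remaining scheduled visits. Footnote a also provides for patients who leave the study at the moment they stop IMP.

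**AE recording.** Protocol 10.4.3 records AEs "spanning from the signature of the informed consent form until the end of the study as defined by the protocol for that patient". After that, Protocol 10.4.4 asks only for serious events that the investigator considers caused by IMP.

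**The concern.** The plan defines a window in which events count as treatment-emergent and justifies it by drug elimination. A reader of the TEAE tables will take it that someone asked each patient about the whole of that window. The visit rules do not guarantee this. One rule lets the last contact come before the window closes. Another removes that contact for patients who stop IMP early, and for some of them nothing scheduled takes its place.

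At stake is the completeness of TEAE ascertainment. Safety is one of the main secondary objectives (Protocol 5.2), and Protocol 8.1.1 sends patients who no longer tolerate their dose after Week 8 into the group without V13. For hypoglycemia, SAP 2.4.5.1 adds one day to treatment duration when it computes exposure. A patient who leaves at an exit visit on the last dosing day therefore contributes that day to the denominator without a planned contact to collect events from it.

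**Working it through.** **Inputs**

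- TEAE window: last injection + 3 days; hypoglycemia: + 1 day (Protocol 9.2.2.1, SAP 2.1.4).
- V13: V12 + 3 days, tolerance -1 to +3 days (Protocol 10.1, 10.1.2.2).
- Last dose in completers: normally the V12 day (Protocol 1.2, 9.2.1.2.2).
- On-site visits from randomization: Weeks 0, 2, 4, 8, 14, 20, 26 (Protocol 1.2).

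**The plan's own figure.** The 3 days are said to be about 5 half-lives, but no half-life is stated, so the figure cannot be reproduced. It can only be inverted: 72 h / 5 = 14.4 h, an implied value.

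**Step 1: completers.** The earliest call is V12 + (3 - 1) = V12 + 2, and the latest is V12 + (3 + 3) = V12 + 6. Counting in whole days, the part of the window left uncovered is the larger of 0 and 3 minus the days from last dose to call.

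| Last dose | Call | Days since last dose | Uncovered days of 3 |
|---|---|---|---|
| V12 day | V12 + 2 | 2 | 1 |
| V12 day | V12 + 3 | 3 | 0 |
| V12 day | V12 + 6 | 6 | 0 |
| Day before V12 | V12 + 2 | 3 | 0 |

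The gap is at most about one day, and arises only when the call is on V12 + 2 and the last dose was on the V12 day. For hypoglycemia the window is 1 day and the earliest call is at day 2, so nothing is uncovered.

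At the implied half-life, 48 / 14.4 = 3.33 half-lives and 0.5^3.33 = 9.9% of drug remains at 48 h. At 72 h it is 0.5^5 = 3.1%. This shows only where day 2 stands against the plan's own rationale for SAR425899. It does not estimate missed events and does not apply to liraglutide.

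**Step 2: patients who stop IMP but stay in the study.** The gaps between on-site visits are 2, 2, 4, 6, 6 and 6 weeks. With a later visit still to come, AE recording passes last dose + 3 days and the window is covered retrospectively.

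**Step 3: patients who leave the study when they stop IMP.** V13 is cancelled and no later visit exists. Footnote a allows for the exit visit to fall on a day when IMP is given. If contact ends on that day, uncovered = 3 - 0 = 3 days, and for hypoglycemia 1 - 0 = 1 day. If the exit visit comes d days after the last dose, with d below 3, the uncovered part is 3 - d days.

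**Step 4: patients who stop permanently k days before V12, k = 1 or 2.** V13 is cancelled and V12 is the last contact. Uncovered = 3 - k, that is 2 days or 1 day. The hypoglycemia window has run out by V12.

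**The case against.** The best defense is that skipping V13 after an early stop is deliberate. V13 is an end-of-study call, and early stoppers are meant to remain in the study. Protocol 10.3.3 follows them to the scheduled end or until any event under follow-up has recovered or stabilized, whichever is later, and Protocol 10.4.3 continues AE observation. This stands. A reader might infer from the cancelled call that all early stoppers go unobserved; for those who stay, the documents say otherwise.

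Three stronger readings also fail:

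- **Recall of up to 6 weeks as a special defect of early stoppers.** Every patient has 6-week gaps between on-site visits after Week 8. Events are classified by onset date, and SAP 2.5.3 treats incomplete onset dates as treatment-emergent unless the available information points elsewhere.
- **Unobserved hypoglycemia in completers.** The 1-day window has closed before the earliest permitted call.
- **Bias between arms.** Events that led to discontinuation began before the stop and are already in scope; only new events in the next 3 days are at issue. The documents give no discontinuation rates, so a loss that differs by dose is conjecture.

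There are other safeguards. Patients are told at V12 to contact the site about any event. Follow-up of known events may run past the last visit (Protocol 10.4.3), and related serious events stay reportable afterwards (Protocol 10.4.4). Protocol 10.3.4 asks withdrawing patients whether AEs contributed to their decision and requires efforts to reach those who fail to return. It is therefore too strong to say that the window is never observed in study leavers. But these measures rely on patients coming forward, look back from the exit visit, or concern patients who did not attend. None is a planned contact at or after the end of the window for someone who attends an exit visit and leaves.

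**Conclusion.** The point holds in limited form and is minor. A fully compliant schedule can end planned AE collection before the declared window closes in three situations:

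1. completers dosed on the V12 day and called on V12 + 2: up to about one day, hypoglycemia unaffected;
2. patients who leave the study when they stop IMP: up to the whole 3 days, including the hypoglycemia day;
3. patients who stop permanently less than 3 days before V12: 1 or 2 days.

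The second group matters most. The calculation counts in whole days and takes the last dose in completers to be on the V12 day, as the flow chart indicates; if it was the day before, the completer gap disappears. The number of patients in each group cannot be derived from the documents, so the effect on TEAE counts cannot be sized. The primary efficacy analysis is unaffected.

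**What to change.** Reconcile the V13 tolerance in Protocol 10.1, the note in Protocol 10.1.2.2, flow-chart footnote a and the exception in Protocol 8.1.1 with the window in Protocol 9.2.2.1 and SAP 2.1.4. The aim is that the last planned AE contact does not precede the end of the declared window for any patient who still consents to contact, including those who leave the study when they stop IMP and those who stop just before V12. How the passages are aligned is the sponsor's decision. The existing V13 phone questions can serve, so no new instrument is needed.

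The cost is protocol wording, one short call for what should be a small number of patients, and possibly a slightly narrower range of days for the call. Patients who stay in the study under scheduled visits need no change.
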